4.7. DATA ANALYTIC PLAN

The primary purposes of a pilot study are to demonstrate safety, acceptability, and feasibility of methods and to determine important parameters with sufficient accuracy to allow reliable estimates of sample size, power, and detectable effects for a subsequent large-scale trial. Parameters include proportions for dichotomous endpoints (i.e. achieved 95% adherence over one-month); means and standard deviations for continuous endpoints (i.e. percentage of adherence over one month); and the spectrum of response profiles for longitudinal studies (i.e. adherence improvement or degradation). Thus, this pilot study aims to ensure that the parameters

for the larger trial are estimated as informatively as possible. We will estimate key study effect parameters with sample means and proportions together with 95% confidence intervals and test the primary null hypothesis at the two-sided level =.05.

5. DATA AND SAFETY MONITORING

The study will collect 5 distinct sources of data: (1) source documents (screening forms, informed consent, and participant contact information [locator form]); (2) assessment data (Baseline, Immediately Post Intervention, 3-month and 6-month Follow-Up Assessments, Biospecimen Acceptability Questionnaire, Self-Reported Adherence Questionnaire); (3) electronic monitoring device (EMD) data; (4) weekly mobile app data; and (5) biospecimen data (viral load test and dried blood spot samples).

Data from source 1 (source documents) will contain identifiable data and will be stored separately from all other data sources, which will only contain coded data. Consent forms from source 1 will be stored in a locked file cabinet in a locked office, and the locator form (which contains the link between patients and their unique PIDs) will be stored in a password protected file on a shared folder through Columbia University's Secure Data Enclave on an encrypted study computer stored in a locked office.

All other data will be labeled only with the PID and will not contain any identifiable information. All data from source 2 (assessment data) will be collected electronically on password protected and encrypted tablets. Data on the tablets will be electronically transmitted to a secure, remote and HIPAA compliant server with partitioned and dedicated space for this study only, known as the 'study server'. Only authorized users will be able to log into the server to view and download data for analysis. The server will maintain an audit trail of all log-ins, edits, and log-outs. Data collected on the tablets can be recorded with or without an internet connection. When there is a connection, the data will be automatically uploaded to the secure study server that will require password authentication. When there is not an internet connection, the data will be cached on the tablet and automatically upload once an internet connection is established. The data will be automatically deleted from the tablet once the upload to the study server is complete and the server will send an automatic email to the project manager and PI indicating that new data have been uploaded. Access to the data collected on the tablets and stored on the study server will be limited to only those study personnel with data access rights. The project manager will monitor the study server weekly to ensure that the data collected and uploaded to the server are complete and to monitor for suspicious data activity.

Data from source 3 (EMD data) and source 4 (mobile app data) will be stored on remote, password protected secure servers and contain no personally identifiable information.

Data from source 5 (biospecimens) will be identified only by the unique PID. Viral load results will be entered into the AIDS Center electronic medical record by clinic staff once the sample is processed. AIDS Center staff will provide a GHRCCA RA with study participant viral load results. DBS results will be processed at the University of Colorado. Hair sample results processed at the University of California-San Francisco.

5.1. Quality Control and Quality Assurance. In collecting the vast majority of the study data electronically, we will be able to closely monitor the quality and completeness of the data in near-real time and strive to correct any mistakes before they are propagated. To ensure that the correct assessment and procedures are completed at each study visit, the data collection program will be programmed to include only the study assessments and procedures relevant to that visit. The data collection program will also require that all questions be answered or refused, and we will build in skip patterns and logic checks for values entered to ensure data quality and completeness. We will closely monitor each step of the specimen collection, transport, storage, and analysis process to ensure that all specimens are continuously accounted for and stored and transported in conditions that will ensure their integrity. The project manager and RA will conduct weekly checks to confirm that the number of specimens collected match the number of assessments completed, and that the number of assessments completed match the number of visits. The research nurse will conduct a weekly check to ensure that the short-term specimen storage conditions are appropriate (e.g., refrigerator and freezer are the correct temperature) and will make adjustments as necessary.

The RA will monitor EMD devices continuously throughout the study to identify those devices that have not been seen by the server in the last week. If after 7 days the device still is not seen at all on the server, the RA will call the participant to see if there are any problems with the device and troubleshoot. The RA will also

conduct an EMD test at each study visit to identify and trouble-shoot any potential problems with the device.

6. HUMAN SUBJECTS PROTECTIONS

6.1. Institutional Review Board/Ethics Committee

This protocol, informed consent form, recruitment materials, and other requested documents will be reviewed and approved by institutional review boards at Columbia University and Al-Farabi Kazakh National University. All study investigators and research staff affiliated with Columbia University will be covered by the Columbia University IRB. All research staff who are not affiliated with Columbia University will be covered by the Al-Farabi Kazakh National University IRB. Subsequent to initial review and approval, the IRBs will review the protocol at least annually. The PI will make safety and progress reports to the IRBs at least annually and after study termination or completion. These reports will include the total number of participants enrolled in the study, the number of participants who completed the study, changes in research activity, and all unanticipated problems involving risks to human subjects or others.

6.2. Informed Consent

Informed consent will be obtained from each study participant prior to conducting study-related procedures. The informed consent process will be conducted in Russian by the Research Assistant (RA). Participants will be told that participation in this study is completely voluntary and their decision whether or not to participate in the study will not affect any medical treatment they are receiving at the clinic or their participation in any other studies being conducted by Columbia University. All study procedures will be described and they will be told that all information will be kept confidential within the limits of the law. Additionally, in the informed consent form, there will be areas for the participant to give permission to contact them for future research studies. Giving permission for this activity is optional not required for participation in the study.

Once the study has been explained in detail, time will be given for participant questions. If the participant wants to join the study, she/he will provide informed consent by signing the informed consent forms. A signed copy will be stored securely in a locked file cabinet in a locked room.

6.3. Risks

Participants enrolled in the study may experience the following risks and discomforts. They will be informed of these potential risks prior to providing their informed consent.

The blood sampling procedures to obtain blood are standard clinic procedures, but have some minor risks. The participant may experience a small amount of pain at the needle-prick site, but this should be minimal. A small amount of bleeding under the skin may produce a hematoma (bruising), which should dissipate in a few days. Venipuncture risks will be minimized by use of sterile technique by a trained nurse. The site of needle-prick will be swabbed with alcohol to minimize the chance of infection and protected by a band-aid or cotton wool to minimize risk of infection and pain. Care will be taken to choose a different needle entry point at subsequent visits. We believe that the likelihood of pain from venipuncture will be small. In previous work among this population, none of the participants reported significant pain from blood sampling procedures and none developed infection as a result of venipuncture.

6.4. Adverse Events

Serious adverse events include death, a life-threatening event, or an event resulting in hospitalization, prolongation of hospitalization, and disability. Serious adverse events, regardless of whether or not they are study-related, will be reported to the Columbia University IRB and the IRB at the study site serving the participant. Other adverse events include breaches of confidentiality (both intentional – e.g., mandated reporting of suicidal/homicidal participants – and unintentional), and non-life threatening psychological distress, arrest by the police and violence. The PI and research staff will closely monitor adverse events. The research team is aware that the study sample is likely to experience some adverse events, though unlikely to be study-related, due to their status in Kazakhstani society, their current or past history of law-breaking activity (e.g., use of or selling of illegal drugs), and the high levels of service needs. Drawing upon past GHRCCA studies, the research team designed an adverse event form.

Study staff will identify, manage and document all adverse events. These events may be identified by RAs, the Project Manager, or other staff, or they may be reported by participants. The procedures used to track, report, and examine adverse events are described below.

- 1) After an adverse event is reported/detected, the study staff member who identified the event will complete an Adverse Event Report form. The report form will include the date, description of the event, duration, severity, measures taken to ameliorate the adverse event, and disposition-related information (e.g., time spent providing referrals and type of referral). The report form will be reviewed and signed by the project manager, [name], and [name], who will be responsible for ensuring that appropriate actions have been taken.
- 2) Drs. [name] and [name] will consult with the Project Manager and any involved staff to ascertain whether the event was related to participation in the study and to ensure that an adequate response is provided to the participant. This will be followed by submission of a report to the IRBs at Columbia University and the Al-Farabi Kazakh National University.
- 3) In the event that a participant withdraws from the study or the PI decides to discontinue a participant due to an adverse event, the participant will be monitored by the Project Manager and the PI via ongoing status assessment until (a) a resolution is reached or (b) the event is determined to be unrelated to the study intervention.

Every two months, the research team from Columbia University and GHRCCA will review all adverse event data to date to determine if systematic trends exist among adverse event data to warrant changes to study protocols and procedures. Any proposed changes will be reviewed with staff at the study site, and, if needed, an external consultant (e.g., other senior investigators conducting federally-funded research on drug abuse). Approval for changes in study protocol or materials will then be obtained from the IRBs at Columbia University and the Kazakhstan School of Public Health. After approval, the NIDA Project Scientist will be notified, and changes will also be reported in the annual progress report submitted to NIDA.

6.4.1. Psychological distress. Participants may experience psychological distress resulting from the assessment questions. Using strategies established in our previous studies, the following steps will be taken to minimize the risk of psychological distress resulting from assessment questions.

1. Participants will be informed that the assessments include questions about sensitive behaviors (e.g., mental health, drug use, sexual behaviors, non-adherence), and that they can decline to answer any questions with which they are uncomfortable.
2. Procedures for emergency and nonemergency situations will involve the RA interviewer informing the project manager and PI of any such incidents of distress so that s/he can monitor compliance with distress-related protocol.
3. Participants who experience mild to moderate distress will be referred to the AIDS Center mental health staff for counseling. We will be able to make immediate referrals as needed to health care providers.

6.4.2. Unintended disclosure. Although it is possible that use of mobile apps or having electronic monitoring devices might also result in inadvertent disclosure of HIV status, we have had no such incidents in a current study (R01-MH09557; PI: [name]; NYPSI IRB# 6451) with over 450 participants using an electronic monitoring device for a 12-month period. Moreover, other colleagues who have used mobile apps or electronic monitoring devices in multiple sites with hundreds of patients have also not had any reported unintended disclosures ([name], [name] personal communication). We will take steps to minimize inadvertent disclosure of HIV status from receipt of text message reminders by keeping the text message simple and without any identifying and/or status related information.

6.4.3. Confidentiality breach. Although study sites will make every effort to protect participant privacy and confidentiality, it is possible that participants' involvement in the study, or information collected by the study, could become known to others, and that participants may experience stigmatization or discrimination as a result. We will take the following steps to protect against the risk of a confidentiality breach.

1. All data, including biosamples, assessments, EMD output, and participant files will be labeled only with study identification numbers, and no participant names will be attached to study data.
2. The participant "key" linking study identification numbers with participant names will be kept by the project manager in a password-protected file on a password-protected and encrypted computer. Only the project manager and authorized research staff will have access to this "key". Personal information including participant's name, address and phone number will be stored separately from research data.
3. Electronic data files will be password protected and stored on a secure study server, which requires authentication to access.
4. All paper research data will be kept in locked file cabinets and will be available only to research staff directly involved in this project and institutional personnel for the purpose of routine audits.
5. All study staff will receive training on procedures to protect participant confidentiality and will take all required courses and certification tests. Participants will be told that all data are confidential within the limits of the law.

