4.6. STUDY PROCEDURES

We will conduct an RCT pilot trial of the adapted couple-based intervention. 66 couples will be randomized into two arms – 33 couples into the intervention arm and 33 couples into standard of care (SOC). SOC consists of an appointment with an AIDS Center nurse at baseline and three and six months later. Under current SOC in Almaty, no behavioral intervention is provided. Participants obtain prescription refills and give blood for viral load and CD4 tests once every 6 months. Participants receive viral load and CD4 test results only by request, and adherence is generally not assessed. We anticipate the intervention will consist of 3 sessions over the course of one month. Participants in both arms will be assessed at 4 time points: baseline “pre-intervention”, immediately post-intervention (IPI), 3-month follow-up, and 6-month follow-up. **Figure 2** illustrates participant flow through the study.

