4.6.3. Immediately Post-Intervention (IPI) Visit (for all participants)

The IPI will be conducted by phone/video call or in-person in GHRCCA’s field office (post-COVID). Prior to the visit, an RA will mail an IPI kit to participants containing materials to self-collect hair and urine samples. For in-person visits, participants will self-collect samples at the GHRCCA field office. The following procedures/assessments will be performed at the IPI visit:

1. The RA will verify the participants by the name on the record and update the **Locator Information Form**;
2. The RA will send the **IPI Assessment** through Qualtrics;
3. The RA will conduct an **EMD** test and will check in with the participant regarding EMD uses and resolve any issues;
4. Participants will self-collect urine samples and hair samples to measure biological levels of medication adherence. These samples will be mailed to GHRCCA staff.
5. At the participant’s next regular AIDS Center visit, the nurse will obtain an additional **blood sample** to conduct dried blood spot sampling and measure levels of medication in the body

4.6.4. 3-month and 6-month Follow-Up Visits (for all participants)

Three- and six-month Follow-Up Visits will be conducted by phone/video call or in-person in GHRCCA’s field office (post-COVID). The following procedures/assessments will be performed at the 3- and 6-month follow-up visits:

1. The RA will verify the participants by the name on the record and update the **Locator Information Form**;
2. The RA will send the **3- or 6-month follow-up assessment** through Qualtrics;
3. At the **3-month** follow-up, the RA will conduct an **EMD** test and will check in with the participant regarding EMD uses and resolve any issues. At the **6-month** follow-up, the participant will mail the **EMD** back to the RA.
4. After the **6-month** follow-up, the RA will administer the Exit Interview;

4.6.5. Pilot study assessments. Participants in both arms will receive the same schedule of assessments. There will be four main repeated assessment occasions: baseline “pre-intervention”, immediately post-intervention (IPI), 3-month and 6-month follow-up. The primary adherence outcome will be proportion of prescribed doses taken as measured by EMD. Study assessments will be delivered remotely through Qualtrics.

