4.6.6. Electronic Monitoring Device (EMD) Data. We will continuously monitor EMD device openings. The EMD sends a signal to a secure website via cellular data networks whenever the device is opened as a proxy for ART adherence. If connection or SIM card problems prevent real-time monitoring, records and diagnostics are stored (up to 1 year) and uploaded to the server when a connection is re-established. The device can store a 30-day supply of medication. EMD-measured adherence will be operationalized as percentage of days/doses for which a device-opening signal was received in the past month. EMDs will be given to participants in both arms. Pills will be deposited into the EMD device, which will record every time the device is opened. EMD data will allow patients to see objective feedback of their adherence patterns, which could help them improve their medication adherence.

At the conclusion of the baseline visit, the RA will mail the participant an EMD device with instructions on how to fill the device, open it for dosing, and pair it with the app. The RA will call the participant to assist with troubleshooting and confirm that the EMD device is properly set up, that it is recognized by the EMD server, and that device openings are being recorded properly (date and time). If 7 days pass and the device is not seen at all on the server, the RA will call the participant to see if there are any device problems. At each study visit, the RA will ask if the participant is having any problems using the EMD.

4.6.7. Weekly app assessments on a mobile phone. Based on GHRCCA’s previous studies, we anticipate that participants will own a smart phone. We will pay for all participants’ data plans during the course of the study. Weekly assessment data will be collected once a week throughout the course of the study through an app which will be installed on participants’ phones. Assessment items will focus on drug use in the past week, adherence to ART, social support, and relationship satisfaction.

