##### 3.2.2. EMD Data.

HIV-positive participants were given an EMD that continuously monitored device openings. The EMD sends a signal to a secure website via cellular data networks whenever the device is opened as a proxy for ART adherence. If connection or SIM card problems prevent real-time monitoring, records and diagnostics are stored (up to 1 year) and uploaded to the server when a connection is re-established. The device can store a 30-day supply of medication.

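### Protocol 6.4, step 3(b): the rule for ending follow-up of people who leave because of an adverse event is, read literally, narrower than step 2's relatedness test (minor wording defect)

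*Protocol*

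**What the plan says.** Protocol 6.4 sets out a three-step procedure for adverse events.

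- Step 1: the staff member who identifies the event completes a report form, which the project manager and study leads review and sign.
- Step 2: the study leads consult the staff involved "to ascertain whether the event was related to participation in the study" and to make sure the participant gets an adequate response. A report to both IRBs follows.
- Step 3 has its own scope: "In the event that a participant withdraws from the study or the PI decides to discontinue a participant due to an adverse event". The project manager and PI then carry out ongoing status assessment "until (a) a resolution is reached or (b) the event is determined to be unrelated to the study intervention".

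The same section expects adverse events in this population, "though unlikely to be study-related". The subsections around it name harms that study procedures could cause: blood sampling (6.3), distress from assessment questions (6.4.1), disclosure of HIV status through apps or monitoring devices (6.4.2) and breach of confidentiality (6.4.3).

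On the arms, section 4.6 says: "Under current SOC in Almaty, no behavioral intervention is provided". Section 4.6.5 says: "Participants in both arms will receive the same schedule of assessments". Section 4.6.6 says: "EMDs will be given to participants in both arms". SAP 3.2.2 limits the device to those with HIV: "HIV-positive participants were given an EMD that continuously monitored device openings".

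**The concern.** Steps 2 and 3 use different objects for relatedness. Step 2 asks about participation in the study; step 3(b) asks about the study intervention. Every event related to the intervention is also related to participation, but the reverse does not hold. An event can therefore be study-related under step 2 and still satisfy the stopping condition in step 3(b).

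The people concerned have just left the study because of an adverse event. If the cause was a study procedure rather than the intervention, the literal text allows ongoing status assessment to end while the harm continues. Some of the named harms, such as stigma after a disclosure, need not resolve quickly. The stake is only that continuing assessment. Staff response, IRB reporting and the two-monthly review of adverse events apply whatever the relatedness finding, and section 6.5 says that those who withdraw may still attend the clinic.

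**Working it through.** There is no figure in the plan to reproduce and no arithmetic to run. The check compares the two tests across the kinds of event the protocol describes. In each case the person has left because of the event, and it is unresolved.

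| Event | Related to participation (step 2)? | Related to the intervention (step 3(b), literal)? | May monitoring stop under literal 3(b)? | Would it stop under step 2's standard? |
|---|---|---|---|---|
| Event with no link to the study | No | No | Yes | Yes |
| Harm arising from an intervention session | Yes | Yes | No | No |
| Distress from assessment questions (6.4.1) | Yes | No | Yes | No |
| Confidentiality breach through study involvement or study data, not through a session (6.4.3) | Yes | No | Yes | No |
| Harm from study blood sampling (6.3, 4.6.8) | Yes | No | Yes | No |
| EMD or app disclosure, standard of care (6.4.2) | Yes | No | Yes | No |
| EMD disclosure, intervention arm (6.4.2) | Yes | Arguable | Depends on the assessor | No |

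1. The two wordings agree in the first two rows. They part only for events related to participation but not to the intervention.

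2. The middle rows are harms that the protocol itself anticipates. Assessment distress is the clearest. Section 4.6.1 lists the baseline assessment ahead of randomization, so distress from it cannot be due to the intervention in either arm. Blood sampling for dried blood spots applies to HIV-positive participants in both arms.

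3. The EMD needs separate treatment by arm. Both arms have it, but in the intervention arm the facilitator goes over the device data with the dyad (4.6.2), and section 4.6.6 describes the data as feedback that could help adherence. A device-related disclosure there could count as intervention-related even on the literal text. In standard of care there are no such sessions. The gap for EMD or app disclosure is therefore clear at least in standard of care.

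4. Does anything else in the protocol fix a different end to follow-up? Section 6.4 says that staff will closely monitor adverse events and that the leads will see to an adequate response, but neither statement gives a duration. Referral to AIDS Center mental health staff for mild to moderate distress (6.4.1) is care, not continuing assessment by the study. Step 3 is the only stated end point after a participant leaves.

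**The case against.** The strongest reply is that this is an editorial slip. Section 6.4 is one numbered sequence, and step 2 is the only relatedness assessment described. No assessor, form or criterion is given for relatedness to the intervention alone, so the determination in step 3(b) most naturally means the one just made in step 2. The protocol also uses the word loosely elsewhere. Section 4.6.1 speaks of randomizing the dyad to an intervention arm and then gives standard of care as one possible result, and section 4.6.11 treats adverse event reporting in general as a matter of intervention safety. This stands as a plausible account of what was meant. It does not settle the matter, because adjacent steps use different phrases and no text equates them. If step 2's standard was meant, the edit only states it.

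The second reply is that the practical effect is slight. Step 3(b) ends a duty and does not forbid further follow-up. Bruising is expected to clear in days, so step 3(a) would normally apply first. The report form records duration and the measures taken, and the leads are responsible for appropriate action on every event. All of this stands, and it is why the point is minor.

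A reader might go further and infer that in standard of care the stopping condition is met automatically for anyone who leaves because of an adverse event, since that arm has no behavioral intervention. The documents do not support this. It needs a strict meaning of intervention that section 4.6.1 does not keep, and a determination must still be made for each event.

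**Conclusion.** The point holds as a minor participant-protection wording defect. As written, step 3(b) permits monitoring of someone who left because of an adverse event to stop while a harm caused by study procedures outside the intervention is unresolved. This rests on the literal text. If step 3(b) was meant to refer back to step 2, the defect is one of expression only.

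The size is small and cannot be turned into a headcount. To be affected, a person must have an adverse event that leads to leaving, that is related to participation but not to the intervention, and that is unresolved when monitoring stops. The documents give no rate for any of these, and the protocol expects events mostly not to be study-related. Counting everyone who completes assessments or carries an EMD would measure exposure, not harm, and would not support a higher grading. Few if any people are likely to be affected.

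A reader might also infer that the trial's safety reporting or its results are compromised. They are not: reporting and review of adverse events do not depend on step 3(b), and no planned estimate, test or sample size changes.

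**What to change.** Reword step 3(b) so that monitoring ends when *the event is determined, under step 2, to be unrelated to participation in the study (the intervention or any study procedure)*. This reuses the existing standard and assessors, and it applies in the same way in both arms.

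The cost is one phrase in section 6.4, with the IRB approval the protocol already requires for changes, and slightly longer follow-up of a few leavers by the project manager and PI. The SAP describes the trial's conduct in the past tense, so the benefit for this cohort may be limited. Section 4.2 says that the pilot is to inform a full-scale efficacy trial, and the corrected wording should be used in that protocol.
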